Prior immunization (PCV13) should have taken place no less than 10 months and no more than 2 years prior to study vaccine administration. Immunogenicity to the 11 non-PCV13 serotypes in PPSV23 will be evaluated. Safety assessments will continue through 30 days postimmunization. Serum samples to measure IgG and OPA levels will be collected prior to study immunization on day 1 and postimmunization on day 30.

Inclusion/Exclusion Criteria:

Inclusion:

A subject is eligible for the study if all of the following apply:

- 1. Institutional Review Board (IRB)/Independent Ethics Committee (IEC) approved written informed consent and privacy language as per national regulations (e.g., Health Insurance Portability and Accountability Act [HIPAA] Authorization for US sites) must be obtained from the subject prior to any study-related procedures (including withdrawal of prohibited medications, if applicable).
- 2. Stage 1: Subject is healthy male or female between 18 and 64 year of age inclusive, at screening.
- 3. Stage 2: Subject is a male or female between 65 and 85 years of age, inclusive, at screening who is healthy or has chronic controlled, stable disease with no change in disease severity, medical therapy and no hospitalization records in last 12 weeks as determined by medical history, physical examination and laboratory data and the clinical judgment of the investigator.
- 4. A female subject is eligible to participate if she is not pregnant (see [Appendix 12.3 Contraception Requirements]) and at least 1 of the following conditions applies:
 - a. Not a woman of childbearing potential (WOCBP) as defined in [Appendix 12.3 Contraception Requirements]
 - b. WOCBP who agrees to follow the contraceptive guidance as defined in [Appendix 12.3 Contraception Requirements] at screening and for at least 28 days after the study vaccine administration.
- 5. Female subject must agree not to breastfeed starting at screening and for 28 days after the study vaccine administration.
- 6. Female subject must not donate ova starting at screening and for 28 days after the study vaccine administration.
- 7. A male subject with female partner(s) of childbearing potential must agree to use contraception as detailed in [Appendix 12.3 Contraception Requirements] at screening and for at least 28 days after the study vaccine administration.
- 8. Male subject must not donate sperm starting at screening and for 90 days after the study vaccine administration.

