- 9. Male subject with a pregnant or breastfeeding partner(s) must agree to remain abstinent or use a condom for the duration of the pregnancy or time partner is breastfeeding at screening and for 28 days after the study vaccine administration.
- 10. Subject agrees not to participate in another interventional study while participating in the present study.

Waivers to the inclusion criteria will **NOT** be allowed.

02 Dec 2019 Astellas Page 18 of 111

Exclusion:

A subject will be excluded from participation if any of the following apply:

- 1. Subject has a known or suspected hypersensitivity to ASP3772, its comparators or any components of the formulations used.
- 2. Subject has had previous exposure with ASP3772.
- 3. Subject has had known previous exposure with PPSV23.
- 4. Subject has received PCV13 or any other licensed or investigational pneumococcal vaccine at any time. (**Note**: This exclusion criterion is not applicable to Group 3; those subjects 65 to 85 years of age who previously received immunization with PCV13. Prior PCV13 immunization should have taken place no less than 10 months and no more than 2 years prior to study immunization. These subjects are eligible to be enrolled in the nonrandomized arm of Stage 2, Group 3).
- 5. Subject has a history of microbiologically-proven invasive disease caused by *Streptococcus pneumoniae*.
- 6. Subject has an immune disorder(s) (including autoimmune disease) and/or clinical conditions requiring immunosuppressive drugs.
- 7. Subject has any evidence of any unstable or active clinically significant cardiovascular, gastrointestinal, endocrine, hematologic, hepatic, immunologic, metabolic, urologic, pulmonary, neurologic, dermatologic, psychiatric, renal and/or other major disease or malignancy, as judged by the investigator, e.g., uncontrolled hypertension, uncontrolled diabetes, heart failure, uncontrolled chronic obstructive pulmonary disease, end-stage renal disease.
- 8. Subject has history of illicit drug(s) or alcohol abuse that the investigator believes will interfere with the protocol requirements and/or a positive urine drug test (for Stage 1 subjects only) at screening.
- 9. Subject has any clinically significant history of allergic conditions including drug allergies, asthma or anaphylactic reactions, but excluding untreated asymptomatic seasonal allergies prior to vaccine administration.
- 10. Subject has a coagulation disorder contraindicating intramuscular immunization.

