- Immunogenicity data will be provided to the investigative site when available to support decision-making for the standard of care.
- k. Sample collection to test for serum anti-biotin antibodies should be repeated at the day 180 visit if tested positive on day 30. Biotin levels will be measured in the same sample if the sample is positive for anti-biotin.
- 1. All concomitant medications or therapies administered from the time the informed consent form (ICF) is signed through day 30 follow-up visit will be collected.
- m. Subject must be under direct supervision for the first 60 minutes following the injection. Local reactogenicity will be evaluated at 1 hour by site staff and entered into the electronic diary by the subject while on site. The subject will evaluate local and systemic reactogenicity symptoms except for joint pain/arthralgia as per Appendix 12.7 daily and record the results on an electronic diary daily through day 7 following the study immunization. On day 7, subject will be questioned if he/she experienced any other illness, which is not incorporated into the reactogenicity assessment, in the electronic diary.
- n. All observed or spontaneously reported AEs, inclusive of MAAEs, PIMMCs and NOCDs will be documented. AEs will be assessed at the study immunization visit, before and approximately 60 minutes after immunization. MAAEs will be reported through day 180. The investigator will avoid leading questions to influence reporting of AEs.

02 Dec 2019 Astellas Page 33 of 111

Table 3 Schedule of Assessments - Stage 2: Subjects 65 to 85 Years of Age and Received PCV13 Within a Year of Randomization (Group 3)

Assessments	Screeninga	Dosing	Follow-up
Visit Number	1	2	3
Visit Day (Window)	-40 to -3	1	30 (±2)
Informed Consent ^b	X		
Inclusion/Exclusion Criteria	X	Χţ	
Vaccine assignment ^c		Χţ	
Demographics	X		
Medical History ^d	X	Χţ	
Physical Examination ^e	X	Χţ	X
Routine 12-lead ECG	X	Χţ	X
Virology ^f	X		
Height, Body Weight	X		
Study Immunization		X	
Vital Signs (blood pressure, pulse rate, body temperature) ^g	X	Χţ	X
Clinical Laboratory Tests (hematology, biochemistry, coagulation profile, hepatic profile, urinalysis) ^h	X	X†‡	X
CCI			
Serum sample for Immunogenicity		Χţ	X
Prior/Concomitant Medication ^j			\rightarrow
AEs^k	<		
SAEs ^k			\rightarrow
MAAEs including PIMMCs and NOCDs ^k			\rightarrow

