of age and 75 to 85 years of age) to ensure there is a balanced number of subjects immunized with ASP3772 or PCV13 with immunogenicity data across the elderly population.

Safety and tolerability assessments including AEs will continue through 30 days postimmunization. Safety assessments for SAEs and MAAEs including PIMMCs and NOCDs will continue through day 180 postimmunization. Data will be collected in an observer-blinded manner (vaccine recipients and the site staff who is responsible for evaluation of any study endpoint will be unaware of which vaccine the subject received).

Serum samples to measure IgG and OPA will be collected prior to study immunization on day 1 and postimmunization on day 30.

Primary immunogenicity evaluation for dose finding is 30 days following the initial immunization.

Stage 2 Group 3:

A separate group of elderly subjects previously immunized with PCV13 will be enrolled and receive the recommended booster immunization with PPSV23 only (n = 99). Prior immunization (PCV13) should have taken place no less than 10 months and no more than 2 years prior to study vaccine administration. Immunogenicity to the 11 non-PCV13 serotypes contained in PPSV23 will be evaluated.

Safety assessments will continue through 30 days postimmunization.

Serum samples to measure IgG and OPA levels will be collected prior to study immunization on day 1 and postimmunization on day 30.

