3.3 Exclusion Criteria

A subject will be excluded from participation if any of the following apply:

- 1. Subject has a known or suspected hypersensitivity to ASP3772 its comparators or any components of the formulations used.
- 2. Subject has had previous exposure with ASP3772.
- 3. Subject has had known previous exposure with PPSV23.
- 4. Subject has received PCV13 or any other licensed or investigational pneumococcal vaccine at any time. (**Note**: This exclusion criterion is not applicable to Group 3; those subjects 65 to 85 years of age who previously received immunization with PCV13. Prior PCV13 immunization should have taken place no less than 10 months and no more than 2 years prior to study vaccine administration. These subjects are eligible to be enrolled in the nonrandomized arm of Stage 2, Group 3.
- 5. Subject has a history of microbiologically-proven invasive disease caused by S. pneumoniae.
- 6. Subject has an immune disorder(s) (including autoimmune disease) and/or clinical conditions requiring immunosuppressive drugs.
- 7. Subject has any evidence of any unstable or active clinically significant cardiovascular, gastrointestinal, endocrine, hematologic, hepatic, immunologic, metabolic, urologic, pulmonary, neurologic, dermatologic, psychiatric, renal and/or other major disease or malignancy, as judged by the investigator, e.g., uncontrolled hypertension, uncontrolled diabetes, heart failure, uncontrolled chronic obstructive pulmonary disease, end-stage renal disease.
- 8. Subject has history of illicit drug(s) or alcohol abuse that the investigator believes will interfere with the protocol requirements and/or a positive urine drug test (for Stage 1 subjects only) at screening.
- 9. Subject has any clinically significant history of allergic conditions including drug allergies, asthma or anaphylactic reactions, but excluding untreated asymptomatic seasonal allergies prior to study vaccine administration.
- 10. Subject has a coagulation disorder contraindicating intramuscular immunization.
- 11. Subject has a positive serology test for hepatitis B surface antigen (HBsAg), hepatitis A virus antibodies (immunoglobulin M), hepatitis C virus antibodies (anti-HCV) confirmed

02 Dec 2019 Astellas Page 47 of 111

- by reflex testing (HCV-RNA) or antibodies to human immunodeficiency virus (HIV) type 1 and/or type 2 at screening.

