- n. All observed or spontaneously reported AEs, inclusive of MAAEs, PIMMCs and NOCDs will be documented. AEs will be assessed at the study immunization visit, before and approximately 60 minutes after immunization. MAAEs will be reported through day 180. The investigator will avoid leading questions to influence reporting of AEs.

Table 3 Schedule of Assessments - Stage 2: Subjects 65 to 85 Years of Age and Received PCV13 Within a Year of Randomization (Group 3)

Assessments	Visit Number	Screening ^a	Dosing	Follow-up
	Visit Day (Window)	1 -40 to -3	2 1	3 30 (±2)
Informed Consent ^b		X		
Inclusion/Exclusion Criteria		X	X†	
Vaccine assignment ^c			X†	
Demographics		X		
Medical History ^d		X	X†	
Physical Examination ^e		X	X†	X
Routine 12-lead ECG		X	X†	X
Virology ^f		X		
Height, Body Weight		X		
Study Immunization			X	
Vital Signs (blood pressure, pulse rate, body temperature) ^g		X	X†	X
Clinical Laboratory Tests (hematology, biochemistry, coagulation profile, hepatic profile, urinalysis) ^h		X	X†‡	X
CCI				
Serum sample for Immunogenicity			X†	X
Prior/Concomitant Medication ^j		↔	↔	→
AEs ^k		↔	↔	→
SAEs ^k		↔	↔	→
MAAEs including PIMMCs and NOCDs ^k		↔	↔	→

AE: adverse event; ECG: electrocardiogram; MAAE: medically attended adverse event; NOCD: new-onset chronic disease; PCV13: Prevnar 13; CCI: ; PIMMC: potential immune-mediated medical conditions; SAE: serious adverse event; WBC: white blood cell.

† To be performed prior to administration of study vaccine. **Note:** Vital signs will also be performed after the administration of the study vaccine.

‡ Not required if collected at a screening visit, which is ≤ 7days from dosing visit.

Footnotes continued on next page

- a. Screening will be completed up to 40 days prior to study immunization. Subjects will be assigned a subject number for use throughout the study at the screening visit via the Interactive Response Technology (IRT) system.
- b. Informed consent must be obtained prior to the performance of any study-related procedure and before assigning vaccine via the IRT system.
- c. Subjects will be assigned a vaccine via the IRT system at the dosing visit.
- d. Medical history will be collected at screening in order to assess Inclusion/Exclusion criteria and will be reconfirmed prior to study immunization.
- e. A physical examination will be performed at screening visit, prior to study immunization (day 1) and day 30 visits.

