The design schematic for Stage 2, Group 2 is shown in the table below. There will be a total of approximately 396 evaluable adult subjects from 65 to 85 years of age.

Number of Subjects per Cohort by Treatment

Cohort	Stage 2 (Group 2)			
	ASP3772	Number of Subjects	Comparator	Number of Subjects
4	1 µg	99	PCV13	33
5	2 µg	99		33
6	5 µg	99		33

PCV13: Prevnar 13

Stage 2, Group 3:

Elderly subjects previously immunized with PCV13 will be enrolled and receive the recommended booster immunization with PPSV23 only (n = 99). Prior immunization (PCV13) should have taken place no less than 10 months and no more than 2 years prior to study drug vaccination. Immunogenicity to the 11 non-PCV13 serotypes contained in PPSV23 will be evaluated. Subjects who are given PPSV23 without previous exposure to PCV13 will not be included in the immunogenicity summaries.

Safety assessments will continue through 30 days postimmunization.

Serum samples to measure IgG and OPA levels will be collected prior to study immunization on day 1 and postimmunization on day 30.

The design schematic for Stage 2, Group 3 is shown in the table below. There will be a total of approximately 99 evaluable adult subjects from 65 to 85 years of age.

Study Treatment Group	Stage 2 (Group 3) Number of Subjects
PPSV23	99

PPSV23: Pneumovax 23

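### Group 3: the waiver of exclusion 4 reaches beyond prior PCV13, the Table 3 titles give a different PCV13 interval from the eligibility text, and the SAP leaves the affected subjects in the summaries

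*Protocol*

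**What the plan says.** **Interval.** The note to exclusion 4 in Protocol 3.3 states: "Prior PCV13 immunization should have taken place no less than 10 months and no more than 2 years prior to study vaccine administration". The synopsis (design overview and its own exclusion 4), Protocol 2.2.1 and SAP 3.2 give the same interval. The title of Table 3, the Group 3 schedule of assessments, differs. In the protocol it is "Subjects 65 to 85 Years of Age and Received PCV13 Within a Year of Randomization (Group 3", and SAP section 2 repeats "Received PCV13 Within a Year of Randomization (Group 3". The exclusion 4 note itself calls Group 3 a nonrandomised arm.

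**Waiver.** Exclusion 4 covers PCV13 and every other pneumococcal vaccine, licensed or investigational, whenever received. Its note says "This exclusion criterion is not applicable to Group 3" and then identifies that group as people aged 65 to 85 with earlier PCV13. Exclusion 2 (ASP3772) and exclusion 3 (known PPSV23) carry no Group 3 exemption.

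**Analysis.** SAP 3.2 adds: "Subjects who are given PPSV23 without previous exposure to PCV13 will not be included in the immunogenicity summaries". The per-protocol exclusions (Protocol 7.2.2, SAP 5.2) concern antibiotics before the Day 30 draw, a late Day 30 draw, immunosuppressants, and new immunological diagnoses. None concerns vaccination history.

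**The concern.** Group 3 serves the second Stage 2 secondary objective: the ASP3772 response read against the PPSV23 response for serotypes not in PCV13. Among its planned summaries are the geometric mean fold rise and the proportion with at least a 4-fold rise, for both IgG and OPA (Protocol 7.4, SAP 7.4.1). Both are relative to baseline, so they depend on the antibody a subject already carries. If an earlier vaccine had exposed a subject to one of those serotypes, baseline could be higher and fold rise lower, and the reference would shift.

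Two pieces of wording bear on who enters that reference. The waiver, read as written, does not stop at the PCV13 part of exclusion 4. The schedule title describes a population that only partly overlaps the one in the eligibility text. Neither the FAS nor the PPS would set aside a subject admitted through either route.

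**Working it through.** **1. Group size.** Stage 2 total = 3 × (99 + 33) + 99 = 396 + 99 = 495, which matches Protocol 7.1. Group 3 is 99 of these. Its size has no precision calculation of its own, so there is no stated figure for this group to recompute.

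**2. The two intervals, in months between PCV13 and study vaccine.**

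| Source | Window | Length |
|---|---|---|
| Design and eligibility text (synopsis, Protocol 2.2.1 and 3.3, SAP 3.2) | 10 to 24 | 14 |
| Table 3 titles (Protocol, SAP), read as 0 to 12 | 0 to 12 | 12 |

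Overlap runs from max(10, 0) = 10 to min(24, 12) = 12, which is 2 months.
- Share of the eligibility window: 2/14 = 14%.
- Share of the title window: 2/12 = 17%.
- Meets the eligibility text but not the title: over 12 and up to 24 months, a span of 12.
- Meets the title but not the eligibility text: under 10 months, a span of 10.

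These are calendar spans, not proportions of subjects. The documents do not give the distribution of intervals among potential Group 3 subjects.

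**3. Which rule covers each vaccination history in a prospective Group 3 subject.**

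| History | Entry rule | Analysis rule |
|---|---|---|
| Prior ASP3772 | Barred by exclusion 2 | Not needed |
| Known prior PPSV23 | Barred by exclusion 3 | Not needed |
| No prior PCV13 | Outside the Group 3 description | Removed from immunogenicity summaries (SAP 3.2) |
| PCV13 outside the stated interval | Contrary to the note, which is worded as a recommendation; no inclusion criterion states it | None: stays in FAS and PPS |
| PCV13 plus another pneumococcal vaccine (not PPSV23 or ASP3772) | Not barred if the note waives all of exclusion 4 | None: stays in FAS and PPS |

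The last two rows are the residue. An out-of-interval subject might be recorded as an entry-criteria deviation (PD1 in Protocol 7.8 and SAP 7.2.2), but PD1 does not remove anyone from a summary. A subject in the last row would not be a deviation at all on the literal reading.

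**4. How wide the last row is.** Stage 2 sites are all in the United States (synopsis). Protocol section 1 describes two pneumococcal vaccines as available there, PCV13 and PPSV23. Protocol 2.2.2 also mentions a 7-valent conjugate, a 10-valent conjugate licensed in Europe, and a 15-valent product in development. It does not say whether any of them contains one of the 11 serotypes evaluated in Group 3. The route is open as worded, but the documents do not show that anyone would use it.

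**The case against.** The strongest reply is that the eligibility rule is consistent. Every design and eligibility statement gives one interval, and the exception is a table title, which is not a criterion. Table 3 has its own row for checking inclusion and exclusion criteria at screening and dosing, which takes a site back to Protocol 3.3, and waivers are prohibited. This stands. A reader might infer that the eligibility criteria contradict each other. They do not.

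On the waiver, the note goes on to define Group 3 by earlier PCV13, so the intent was probably to lift only that part, and exclusions 2 and 3 close the most relevant routes. This also stands as a limit on size, but the literal wording still waives the whole criterion.

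A reader might also infer that a short PCV13 interval distorts the Group 3 results. The documents do not support that. The endpoints cover only serotypes outside PCV13, and the one related statement, from rabbit data in Protocol 2.2.2, is that PCV13 produced no response to them.

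Finally, the SAP 3.2 rule might be read as proof that the entry criteria fail to prevent mis-enrolment. SAP section 8 describes the people concerned as subjects who ought to have had PCV13, so the rule handles departures from an existing requirement. It does show that the SAP addresses one kind of departure and not the others.

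**Conclusion.** The point holds in a limited form. As worded, the exclusion 4 note admits to the PPSV23 reference group subjects it was evidently not meant to admit. The Table 3 titles in both documents conflict with the stated interval and with the group being nonrandomised. The SAP screens out only one of the three kinds of unsuitable vaccination history that remain after exclusions 2 and 3.

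The firm figure is the 2-month overlap, and it assumes the title is read as 0 to 12 months. The waiver gap assumes the note is read literally, and it is narrow. The effect on GMFR or on 4-fold response cannot be estimated: the documents give neither the number of subjects involved nor the response such subjects would show.

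A reader might go further and conclude that the reference group is not the group the protocol describes. That does not follow. Enrolment under Protocol 3.3, together with the SAP 3.2 rule, gives a prior-PCV13 group as described, with a possible but unquantified admixture. The correction is worth making because Group 3 has no other purpose than to be this reference. The title alone would be close to clerical.

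**What to change.** (a) Reword the note to exclusion 4, in Protocol 3.3 and the synopsis, so that only the prior-PCV13 part is waived for Group 3 and the bar on other licensed or investigational pneumococcal vaccines remains.

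(b) Reconcile the Table 3 titles with the eligibility text so that one interval applies throughout the protocol and SAP, and replace the reference to randomisation with enrolment or vaccination. Which interval applies is for the sponsor to settle; this review takes no position.

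(c) In the SAP, add a supportive Group 3 immunogenicity summary that leaves out subjects outside the reconciled interval and subjects with another prior pneumococcal vaccine. The FAS summary stays as the main one. If Group 3 enrolment is already under way, (c) is the part that deals with subjects already admitted.

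The cost is wording in two documents, slightly narrower Group 3 eligibility, and one extra summary. The PCV13 date is already needed to apply the existing interval.

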1 INTRODUCTION

Streptococcus (S.) pneumoniae is a significant cause of morbidity and mortality among infants, young children, the elderly and individuals who have certain underlying medical conditions. S. pneumoniae remains a leading cause of serious illness, including bacteremia, meningitis and pneumonia among children and adults worldwide. It is also the most frequent cause of sinusitis and acute otitis media [CDC, 2010]. Pneumococcal disease can cause both invasive and noninvasive disease. The most common form of noninvasive disease, nonbacteremic pneumococcal pneumonia, remains one of the most frequent disease manifestation accounting for pneumonia hospitalizations. Invasive pneumococcal disease (IPD) is defined as S. pneumoniae isolated from a normally sterile site (e.g., cerebrospinal fluid, blood, joint fluid, pleural fluid or peritoneal fluid). The highest incidence of IPD is found at the extremes of age – in elderly adults and in young children < 2 years of age. S. pneumoniae causes approximately 17000 cases of invasive disease each year among children younger than 5 years of age, including 700 cases of meningitis and 200 deaths [CDC, 2000]. The highest morbidity and mortality rates have been reported in developing countries, but the disease burden is also considerable in industrialized countries.

Two different vaccines for *S. pneumoniae* are currently available in the US. PCV13, a 13-valent conjugate vaccine, has been approved for the prevention of IPD caused by the 13 serotypes contained in the vaccine in children and for the prevention of pneumonia and IPD in adults. In this vaccine, conjugation of pneumococcal saccharides to the CRM197 protein creates a saccharide-protein complex, which is capable of inducing a T-dependent immune response; thus, T helper cells are stimulated, leading to a substantial primary response and a strong booster response at re-exposure [PREVNAR 13 prescribing information, 2017]. However, there are > 90 serotypes of *S. pneumoniae*, and PCV13 provides protection only against those 13 serotypes contained in the vaccine. While infections with *S. pneumoniae* of multidrug-resistant serotypes, which are contained in PCV13 decreased after availability of this vaccine, an increase of infections with multidrug-resistant serotypes 35B, 23A, 23B and 15B, which are not included in PCV13, was noted. Also, PCV13 appeared to have marginal activity against serotype 3, as its prevalence persists in the population [Richter et al, 2014].

The second vaccine, Pneumovax[®]23 (PPSV23), is a 23-valent polysaccharide (PS) vaccine and is indicated for the prevention of pneumococcal disease in adults ≥ 50 years of age or in persons ≥ 2 years of age at increased risk of pneumococcal disease. It is composed of purified capsular PS from 23 pneumococcal serotypes. While this vaccine protects against more serotypes when compared to PCV13, it does not provide protection against the emerging serotypes 35B, 23A and 23B. In addition, PPSV23 elicits a T-independent PS immune response that stimulates mature B-lymphocytes, but not T-lymphocytes, and induces an immune response that is neither long-lasting nor anamnestic upon subsequent challenge. In addition, PS-type vaccines are not used in infants and children < 2 years of age, because these children respond poorly to T-independent antigens [Pneumovax 23 prescribing information, 2017; CDC, 2010]. Data suggest that PPSV23 protects adults and the elderly against IPD; however, no consistent effect has been observed in the prevention of pneumonia [Gruber et al, 2008].

Thus, there is a medical need for a vaccine that provides T-cell dependent immunity against a broad range of serotypes of *S. pneumoniae*.

